2.8.4 Other safety data

2.8.4.1 ECG and cardiac imaging data

The ECG measurements from this clinical study will be performed as per standard of care for routine safety monitoring, rather than for purposes of assessment of potential QTc effect. Subject incidence of abnormal ECG diagnosis (see [Table 2-7](#)) will be summarized by treatment group and by visit for initially assigned treatment.

ECG measurements with abnormalities will be listed by treatment.

However, since these evaluations may not necessarily be performed under the rigorous conditions expected to lead to meaningful evaluation of QTc data, these data are not expected to be useful for meta-analysis with data from other trials.

Table 2-7 ECG Abnormality Ranges

ECG Parameter	Abnormality Flags	
	Absolute	Relative*
RR Interval	Low: < 600 msec ; High: > 1200 msec	Low: $\leq -20\%$; High: $\geq 20\%$
PR interval	Low: < 120 msec ; High: > 200 msec	Low: $\leq -20\%$; High: $\geq 20\%$
QRS Interval	Low: < 60 msec ; High: > 109 msec	Low: $\leq -20\%$; High: $\geq 20\%$
QT Interval	Low: < 320 msec ; High: > 450 msec	Low: $\leq -20\%$; High: $\geq 20\%$
QTcB Interval (Bazett's correction)	Low: < 320 msec ; High: > 450 msec	Low: $\leq -20\%$; High: $\geq 20\%$
QTcF Interval (Fridericia's correction)	Low: < 320 msec ; High: > 450 msec	Low: $\leq -20\%$; High: $\geq 20\%$

*Relative change from previous measurement in percent (%)

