4.5 Risks and benefits

Key risks and benefits are briefly summarized below. For further information, please refer to the current package insert/prescribing information and the Investigator Brochure.

As of June 2018, the safety of erenumab in migraine prophylaxis was assessed from integrated safety analyses of 2537 migraine patients exposed to at least one dose of erenumab, with a cumulative exposure of 2310.3 subject-years (SY). Overall, the safety and tolerability profile of erenumab was similar between the 140 mg and 70 mg doses and comparable to placebo. Adverse drug reactions include injection site reactions, constipation, muscle spasms, and pruritus. The majority were mild or moderate in severity and rarely led to treatment discontinuation. To date, no important risk has been identified for erenumab.

Overall, to date, there is no evidence from non-clinical and clinical data of risk of cardiovascular effects. On the theoretical basis of the mechanism of action of erenumab, CGRP receptor blockade might reduce compensatory vasodilation, particularly under ischemic conditions. Therefore, cardiovascular effects continue to be monitored.

Plasma levels of CGRP increase with advancement of pregnancy up to the time of delivery, followed by a sharp decline at term and postpartum in rats and humans. Endogenous CGRP may play an important role in maintaining normal fetoplacental development, fetal survival, and vascular adaptation during pregnancy. Women who are breastfeeding, pregnant, or planning to become pregnant are excluded from study participation, as well as patients who are unwilling to comply with the protocol-specified contraception requirements. All women of child-bearing potential will be screened for pregnancy at each study visit.

An external data monitoring committee was established to review the erenumab safety data for Phase 2b and Phase 3a studies, and based on these data, recommended continuation of the program. The need for a data monitoring committee (DMC) for this study was assessed, and deemed not necessary because erenumab was approved by FDA and EMA for migraine prophylaxis and the safety profile of erenumab was well characterized in 4 double-blind, placebo-controlled trials in over 2500 patients. The risk to patients in this trial will be minimized by compliance with the eligibility criteria, close clinical monitoring, and allowance of acute rescue medications.

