8.4.2 Electrocardiogram (ECG)

ECGs will be recorded as outlined in the central ECG reading manual. The preferred sequence of cardiovascular data collection during study visits is ECG collection first, followed by vital signs, and blood sampling. The Fridericia QT correction formula (QTcF) as reported by the central reader should be used for clinical decisions.

Single 12 lead ECGs will be collected. The original ECGs printed on non-heat sensitive paper, appropriately signed, must be collected and archived at the study site.

Each ECG tracing must be labeled with study number, patient initials, subject number, date and time, and filed in the study source documents. For any ECGs with patient safety concerns, two additional ECGs must be performed to confirm the safety finding and forwarded to the central ECG laboratory for assessment. Clinically significant ECG findings pre-dose must be discussed with the sponsor before administration of study treatment.

Clinically significant abnormalities must be recorded on the relevant section of the medical history/current medical conditions/AE eCRFs as appropriate.

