2.1.1.4 Baseline

The baseline period for efficacy analysis is defined as the period between week -4 visit (when eDiary device is dispensed to the subject for daily data capture) and the day prior to study day 1 (study day 1 is not included).

A baseline for subject reported outcome (PRO) and safety (including Columbia-Suicide Severity Rating Scale (C-SSRS)) values refers to the last evaluable measurement prior to the first administration of the study drug, irrespective of re-screening. In this case, baseline values will be the value obtained on the day of the randomization (Day 1, Visit 101), or on an earlier visit (scheduled or unscheduled) which is the closest to Visit 101, if Visit 101 is missing or the assessment was not done at baseline.

Baseline weight and height are taken from vital signs screening visit.

eCSSRS is collected at screening or before randomisation and patients should complete “lifetime assessment eCSSRS questionnaire” at screening and if need arises during the course of the trial complete “since last contact eCSSRS questionnaire”. Hence, we do not have “Evaluation timeframe” (TMFRM) variable collected and baseline eCSSRS will correspond to the last evaluable measurement prior to the first administration of the study drug, irrespective of re-screening. For this analysis, each subject can only be counted once for each event. However, a subject can be counted in several different events.

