2.1.1.6 Visit remapping and assessment windows

Since the actual visit for a subject may not exactly coincide with their targeted visit date, the actual visit date is mapped to a study visit. Also note that month 6 is equivalent to week 24, and month 12 is equivalent to week 52.

The next study day window will be utilized to define study visit for lab, vital signs, C-SSRS and [REDACTED] PROs collected during office visits [REDACTED] before dose is administered.

Table 2-1 Study visit windows

Study visit	Target Day	Study Day
Baseline	Please refer to Section 2.1.1.4 .	
Week 4	28	16-43

Week 8	56	44-71
Week 12	84	72-99
Week 16	112	100-127
Week 20	140	128-155
Week 24	168	156-183
Week 28	196	184-198
Week 32	224	199-239
Week 36	252	240-267
Week 40	280	268-295
Week 44	308	296-323
Week 48	336	324-351
Week 52	364	352-379
Safety follow up	Safety follow-up should be excluded from the analysis visit windows described above and summarized under 'safety follow-up' for safety analyses only. Refer to Table 2.2 .	

Note: xx: target day then study day window: (xx-12 days) up to (xx+ 15 days)

For efficacy parameters: If more than one visit (including the unscheduled visits) fall within the same defined window with non-missing measurements, scheduled visit will be used regardless of the distance from the target day. Unscheduled visit will only be used when there is no measurement from scheduled visit in the defined window. The closest visit to the target day among the same type of visit (i.e., closest of all scheduled visits or if no scheduled visits, closest of all unscheduled) will be considered for analysis. If two assessment dates are equidistant from the target date, the latter assessment will be considered for analysis. The exception is an assessment at early study withdrawal visits along with another assessment within a window. In such cases the early-withdrawal assessment will be used.

For safety parameters: in case of competing assessments within a analysis window, the last one closest to the scheduled visit day will be used.

Table 2-2 Study intervals for safety analysis

	Start time point	End time point

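### The relative ECG flag in SAP Table 2-7 is measured against the previous ECG instead of baseline, so the Week 52 incidence can miss, drop or wrongly count changes (minor, descriptive safety only)

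*SAP*

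**What the plan says.** Table 2-7 in SAP section 2.8.4.1 gives each of six ECG parameters two kinds of flag. The absolute flag has its own limits per parameter (for PR, "Low: < 120 msec ; High: > 200 msec"). The relative flag is the same for all six: a change of -20% or lower, or +20% or higher. The footnote defines that change as "Relative change from previous measurement in percent".

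The table feeds an analysis as well as a listing: "Subject incidence of abnormal ECG diagnosis (see [Table 2-7](#)) will be summarized by treatment group and by visit for initially assigned treatment".

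Elsewhere the SAP works from baseline. Section 2.1.1.4 says that a safety baseline "refers to the last evaluable measurement prior to the first administration of the study drug". Laboratory results are summarised as change and shift from baseline (2.8.3), and every change criterion for pulse and blood pressure in Table 2-8 is from baseline (2.8.4.2). Nothing in the SAP redefines the previous measurement as baseline, and no reason is given for treating ECG differently.

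Protocol Table 8-1 schedules ECGs at Screening, at one mid-study visit and at Week 52, with none on Day 1. Protocol section 12.5.2 says only that ECG abnormalities will be flagged, without naming a reference. It also promises a listing of all ECG data and summary statistics by treatment.

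**The concern.** For a scheduled mid-study ECG, the previous scheduled measurement is the Screening ECG, which is also the baseline, so the two references agree. At Week 52 the previous measurement is the mid-study ECG. One by-visit incidence table therefore answers two questions: change since before treatment at the first visit, and change since mid-treatment at the second.

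At Week 52 this can misclassify a subject in three ways. A gradual change can pass unflagged because neither step is large enough. A change that appears mid-study and persists drops out of the Week 52 count, which reads as resolution. A value that moved and came back can be counted as a new abnormality, in the opposite direction to the change.

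What is at stake is how far a safety table can be trusted. Protocol section 4.5 describes a theoretical vascular risk and says: "Therefore, cardiovascular effects continue to be monitored". A reader who compares arms by visit would expect the Week 52 row to mean different from baseline.

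**Working it through.** The plan states no figure to reproduce, so the check applies the Table 2-7 rules to short ECG sequences.

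**Inputs from the documents.** Relative threshold of 20% in either direction. Absolute limits in msec: RR 600 to 1200, PR 120 to 200, QRS 60 to 109, QT and QTc 320 to 450. Scheduled ECGs at Screening (x0), mid-study (x1) and Week 52 (x2).

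**Assumptions.** The msec sequences are illustrative, not trial data. Either kind of flag counts as abnormal, and no unscheduled ECG falls between the scheduled ones.

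**Formulas.** As written: 100 × (x2 - x1)/x1. Against baseline: 100 × (x2 - x0)/x0. At mid-study both are 100 × (x1 - x0)/x0.

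Every value below lies inside its absolute limits.

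| Sequence (msec) | Mid-study | Week 52 as written | Week 52 from baseline |
|---|---|---|---|
| PR 150, 170, 190 | +13.3% | +11.8%, no flag | +26.7%, flag |
| QRS 80, 92, 104 | +15.0% | +13.0%, no flag | +30.0%, flag |
| QTcF 370, 408, 446 | +10.3% | +9.3%, no flag | +20.5%, flag |
| RR 1000, 810, 657 | -19.0% | -18.9%, no flag | -34.3%, flag |
| PR 150, 190, 190 | +26.7%, flag | 0%, no flag | +26.7%, flag |
| PR 150, 190, 150 | +26.7%, flag | -21.1%, flag Low | 0%, no flag |
| RR 900, 700, 850 | -22.2%, flag | +21.4%, flag High | -5.6%, no flag |
| RR 1200, 1000, 1200 | -16.7% | +20.0%, flag High | 0%, no flag |
| PR 150, 180, 150 | +20.0%, flag | -16.7%, no flag | 0%, no flag |

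**Largest missed drift.** Two steps just under the threshold give 1.20 × 1.20 = 1.44 and 0.80 × 0.80 = 0.64, so just under +44% or -36% from baseline. The absolute limits narrow this for QT and QTc: a value that starts and ends inside 320 to 450 can rise by at most 450/320 - 1 = 40.6% and fall by at most 1 - 320/450 = 28.9%.

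**Where the absolute flag does not help.** A 20% rise stays inside the upper limit when baseline is at most 200/1.2 = 166.7 (PR), 109/1.2 = 90.8 (QRS), 450/1.2 = 375 (QT, QTc) or 1200/1.2 = 1000 msec (RR). Above those baselines the absolute flag catches it: QTcF 400, 440, 480 is flagged High at 480.

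**When a return is flagged.** A full return after a rise of fraction r is a change of 1/(1 + r) - 1. This reaches -20% when r is at least 1/0.8 - 1 = 25%. After a fall of fraction f the change is 1/(1 - f) - 1, which reaches +20% when f is at least 1 - 1/1.2 = 16.7%. The last two rows of the table show the asymmetry: a 16.7% fall is not flagged but its reversal is, while a 20% rise is flagged and its reversal is not.

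**The case against.** Much can be said for leaving this alone, and several parts of that case stand.

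For scheduled ECGs the two references differ only at Week 52. The absolute flags do not depend on the reference. Protocol section 12.5.2 promises a full ECG listing and summary statistics. SAP section 2.8.4.1 does not repeat those outputs, but the SAP introduction says analysis follows protocol section 12, and SAP section 4 declares no change to protocol-specified analyses. Drift would therefore remain visible elsewhere, and it would go too far to infer that such findings vanish from the report.

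The RR example also overlaps with vital signs. RR 1000 to 657 msec is 60000/1000 = 60 to 60000/657 = 91 beats per minute, and Table 2-8 already flags a pulse change of 15 or more from baseline. That cover does not extend to PR, QRS or QT.

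A reader might also infer that a change confirmed by repeat ECG is lost. Protocol section 8.4.2 says: "For any ECGs with patient safety concerns, two additional ECGs must be performed to confirm the safety finding". SAP section 2.1.1.6 says of safety parameters that "in case of competing assessments within a analysis window, the last one closest to the scheduled visit day will be used". If the last repeat were analysed and compared with the repeat just before it, a confirmed change would score near 0%. The documents do not establish this. The visible text of 2.1.1.6 does not name ECG among the assessments given visit windows. Section 8.4.2 gives no timing for the repeats. If one record per visit is selected before flags are derived, the comparison is with the prior visit. On any reading, a first ECG that meets the threshold is still flagged and listed. This is a possible further consequence, not a demonstrated error.

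Nor do the documents support reading the footnote as a failure of cardiovascular monitoring. The risk in protocol section 4.5 is reduced compensatory vasodilation, particularly under ischaemic conditions, and is not tied to percentage changes in ECG intervals. Adverse events, blood pressure and pulse against baseline, and a hypertension summary are also planned. The SAP says the ECGs serve routine monitoring and are not meant to assess a QTc effect.

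None of this supplies a reason for the previous-ECG reference or removes the mixed meaning of the by-visit table.

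**Conclusion.** The point holds, and its severity is minor. As written, the relative flag at Week 52 can miss a two-step change of up to just under +44% or -36% from baseline, can show a sustained change as resolved, and can flag a return to baseline after a rise of at least 25% or a fall of at least 16.7%. These are things the rule can do; how often they would occur cannot be judged from the documents.

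The conclusion rests on taking the footnote literally, on the ECG schedule in protocol Table 8-1, and on the relative flag counting towards the incidence of abnormal ECG. It affects one descriptive safety summary and its listing. No hypothesis test, efficacy endpoint or analysis set depends on it.

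**What to change.** In the Table 2-7 footnote, replace the previous measurement with baseline as defined in SAP section 2.1.1.4. State that the same reference applies to any repeat or unscheduled ECG; this also settles the question about confirmatory repeats, whichever record is selected.

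If the sponsor has a reason to keep the previous-measurement flag, give that reason in section 2.8.4.1 and add a change-from-baseline summary by visit, so that the Week 52 row can be interpreted.

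The cost is one footnote and about one line of programming. All the data are already collected, and no visit, assessment or other analysis changes.

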2.8.4.2 Vital signs

The vital signs data is collected prior to dosing. The analyses of vital signs (systolic/diastolic blood pressure, pulse rate) and weight will include summary statistics of change from baseline by treatment group and by visit for initially assigned treatment.

The number and percentage of subjects with clinically relevant abnormality (see [Table 2-8](#)) at any post-baseline visit will be presented for initially assigned treatment. This vital sign data will also be listed.

Table 2-8 Vital Signs Notable Criteria

Vital Sign Variable	Notable Criteria
Pulse (beats/min)	> 120bpm or Increase of ≥ 15 bpm from baseline Or < 50bpm or Decrease of ≥ 15 bpm from baseline

Systolic BP (mmHg)	>180 mm Hg or Increase of ≥ 20 mm Hg from baseline Or < 90 mm Hg or Decrease of ≥ 20 mm Hg from baseline
Diastolic BP (mmHg)	> 105 mmHg or Increase of ≥ 15 mm Hg from baseline Or < 50 mmHg or Decrease of ≥ 15 mm Hg from baseline

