Subjects should be seen for all visits/assessments as outlined in the assessment schedule or as close to the designated day/time as possible. Missed or rescheduled visits should not lead to automatic discontinuation. Subjects who prematurely discontinue the study for any reason should be scheduled for a visit as soon as possible, at which time all of the assessments listed for the final visit will be performed. At this final visit, all dispensed investigational product should be reconciled, and the adverse event and concomitant medications recorded on the CRF.

Treatment discontinuation does not imply study discontinuation. Every effort should be attempted to ensure subjects complete the study visits event if treatment is discontinued.

If the **COVID-19 pandemic** limits or prevents on-site study visits, alternative methods of providing continuing care may be implemented. Phone calls, virtual contacts (e.g. teleconsult) or visits by site staff to the participant's home depending on local regulations and capabilities, can replace on-site study visits, for the duration of the pandemic until it is safe for the participant to visit the site again (see [Section 8.3](#) efficacy, [Section 8.4.1](#) Laboratory evaluations, [Section 8.4.3](#) Pregnancy, [Section 8.5.3](#) [REDACTED] and [Section 8.4](#) Safety monitoring.

Table 8-1 Assessment Schedule – Core Phase

Period	Screening			Open Label Randomized Treatment													
Visit Name	Screening	Baseline	Treatment	Week 4	Week 8	Week 12	Week 16	Week 20	Week 24	Week 28	Week 32	Week 36	Week 40	Week 44	Week 48	Week 52 / Early Exit ¹⁰	
Days	-42 to -28		-28 to -1		Day 1	28	56	84	112	140	168	196	224	252	280	308	364
Weeks	-6 to -4		-4 to -1		1	4	8	12	16	20	24	28	32	36	40	44	52
Informed consent	X																
Medical history/current medical conditions	X																
Demography	X																
Physical Examination ¹	X	X	X	X	X	X	X	X	X	X	X	X	X	X	X	X	X
Vital signs and body measurements	X	X	X	X	X	X	X	X	X	X	X	X	X	X	X	X	X
Electrocardiogram (ECG)	X									X							X
Pregnancy Test (serum) ²	X																X
Pregnancy test (urine) ²		X	X	X	X	X	X	X	X	X	X	X	X	X	X	X	X
Central blood chemistry - Erenumab	X		X							X							X
Central blood chemistry – SoC Oral Prophylactics ³	X		X	X ³	X ³	X ³	X ³	X ³	X	X ³							
Urine Drug Screen	X																
Columbia-Suicide Severity Rating Scale (C-SSRS) ⁴	X																
Randomization			X														
Study drug administration ⁵			X	X	X	X	X	X	X	X	X	X	X	X	X	X	X

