Contact IRT	X	X	X	X	X	X	X	X	X	X	X	X	X	X	X	X	
Clinical Outcome Assessment(s) ⁶		X	X	X	X	X	X	X	X	X	X	X	X	X	X	X	X
Patients' Global Impression of Change						X				X			X		X		X

Period	Screening			Open Label Randomized Treatment													
	Visit Name	Screening	Baseline	Treatment	Week 4	Week 8	Week 12	Week 16	Week 20	Week 24	Week 28	Week 32	Week 36	Week 40	Week 44	Week 48	Week 52 / Early Exit ¹⁰
Days	Days	-42 to -28	-28 to -1	Day 1	28	56	84	112	140	168	196	224	252	280	308	336	364
Weeks	Weeks	-6 to -4	-4 to -1	1	4	8	12	16	20	24	28	32	36	40	44	48	52
Adverse Events ⁹				X	X	X	X	X	X	X	X	X	X	X	X	X	X
Serious Adverse Events ⁹	X	X	X	X	X	X	X	X	X	X	X	X	X	X	X	X	X
Concomitant medications	X	X	X	X	X	X	X	X	X	X	X	X	X	X	X	X	X
Concomitant therapies	X	X	X	X	X	X	X	X	X	X	X	X	X	X	X	X	X
Core phase ¹⁰ completion																	X

^x Assessment to be recorded in the clinical database or received electronically from a vendor

¹ Full exam at Screening, Week 52. Height and weight will be measured at full exam. Short physical exam at all other visits.

² Results of pregnancy tests (serum or urine) will be captured as source and not in eCRF.

³ For subjects randomized to SoC oral prophylactics, central blood chemistry must be done at Screening, Treatment, Week 24, Week 52. All other visits, central blood chemistry to be done as needed for monitoring. Any additional safety measurements, if applicable, should be implemented as per label.

⁴ C-SSRS will be the electronic C-SSRS designed for computer administration (web or phone)

⁵ At every monthly study visit, the investigator should assess tolerability to randomized treatment (erenumab or SoC oral prophylactics) and determine if switching is appropriate. At Week 48, this will be the last dose of erenumab for subjects randomized to erenumab (monthly treatment). SoC oral prophylactics will continue to be dosed through month 12 as per label.

⁶ Patients will record migraine, headache, and headache medication information daily using the provided electronic diaries.

⁹ AE to be captured from Day 1 onward and SAE collection will be captured after informed consent is obtained.

¹⁰ Patients that complete Core Phase visits through Week 52 may be eligible to enter the Extension Phase. All patients will receive erenumab during the Extension Phase.

Table 8-2 Assessment Schedule – Extension Phase

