Height & weight	Height in centimeters (cm) and body weight (to the nearest 0.1 kilogram (kg) in indoor clothing, but without shoes) will be measured during full physical exams.
Columbia Suicide Severity Rating Scale	See Section 10.2.2

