9.1.2 Discontinuation of study

For patients that will discontinue from the study they need to complete the Early Exit Visit / Week 52 visit at the time of study discontinuation.

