	date in PTA phase	
2. If subject discontinues prior to completing 52 weeks on treatment in PTA phase i.e. treatment disposition reason is not equal to “COMPLETED” on DS domain then
 
 If treatment disposition date > treatment end date plus 27 day then use trt end date plus 27 day If treatment disposition date <= treatment end date plus 27 day then use trt disposition date
--	-------------------	--

	Start time point	End time point
Initially assigned treatment (IAT) period (core phase)	Treatment start date	
1. Subject completes 52 weeks on IAT i.e. core phase treatment disposition reason is “COMPLETED” and week 52 visit date is non-missing in SV domain and date of switching is missing on DS domain
 
 If subject does not enter PTA phase then use week 52 visit date from SV domain If subject enters PTA phase then 
 i. Subject enters PTA on week 52 visit date then use a day prior to week 52 visit date ii. Subject enters PTA phase after week 52 then use week 52 visit date 
2. Subject completes 52 weeks on core phase but permanently discontinues IAT early i.e. trt disposition reason is not equal to “COMPLETED” on DS domain and week 52 visit date is non-missing in SV domain and date of switching is missing on DS domain
 
 If subject does not enter PTA phase 
 i. if week 52 visit date > treatment end date plus 27/1 day then use treatment end date plus 27/1 day ii. if week 52 visit date <= treatment end date plus 27/1 day then use week 52 visit date If subject enters PTA phase 
 i. if week 52 visit date > treatment end date plus 27/1 day then use treatment end date plus 27/1 day

		
 ii. if week 52 visit date \leq treatment end date plus 27/1 day then use a day prior to first dose in PTA phase 3. Subject does not complete 52 weeks on study and permanently discontinues IAT i.e. week 52 visit date is missing in SV domain and date of switching is missing on DS domain and core phase treatment disposition reason is not equal to "COMPLETED in DS domain then use min(trt disposition date, trt end date plus 27/1 day) 4. Subject switches IAT then use day prior to date of first switch on DS domain

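### The SAP weight summary for initially assigned treatment can leave out Week 52 values of subjects who switched or stopped, and of completers entering post-trial access

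*SAP*

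**What the plan says.** **Measurement.** Protocol Table 8-1, footnote 1, states: "Full exam at Screening, Week 52. Height and weight will be measured at full exam. Short physical exam at all other visits". Table 8-3 agrees that height and weight "will be measured during full physical exams". The row "Vital signs and body measurements" in Table 8-1 is marked at every visit, but the footnote limits weight to the full exams. The Week 52 column doubles as Early Exit. Protocol 9.1.2 ties that visit to leaving the study: such subjects are told "they need to complete the Early Exit Visit / Week 52 visit at the time of study discontinuation". Stopping or switching the drug does not trigger it, and Protocol 3, 8 and 9.1.1 ask subjects who stop treatment to keep attending visits. Baseline weight is the screening value (SAP 2.1.1.4).

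**Analysis.** SAP 2.8.4.2 says that the analyses of blood pressure, pulse and "weight will include summary statistics of change from baseline by treatment group and by visit for initially assigned treatment". SAP Table 2-2, which sets the intervals for safety analysis, closes the IAT period under this rule: "Subject switches IAT then use day prior to date of first switch on DS domain". For subjects who stop without switching, the period generally closes 27/1 days after the last dose. For completers who enter post-trial access (PTA) on the Week 52 visit date, it closes the day before that visit. SAP 2.8.4.1 says that abnormal ECG incidence "will be summarized by treatment group and by visit for initially assigned treatment".

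**The concern.** Switching is left to investigator and subject on grounds of efficacy, tolerability and satisfaction (Protocol 3). A subject who leaves the first drug because it is poorly tolerated may therefore be gone before the one scheduled weight. If the summary uses only IAT-period data, it describes a selected group, and the share selected out probably differs between arms. The between-arm contrast in weight change would then not be a comparison of the groups as randomised. If the phrase only names the arm, the oral Week 52 weights belong partly to drugs started later, and the first drug is still unmeasured in those who switched. SAP 2.8.1 and 2.4.2 plan separate outputs for switched treatment for adverse events and concomitant medication. No such output is named for weight, and Table 2-8 has no weight criterion that would catch a change at any visit.

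**Working it through.** **Step 1: which weights fall inside the IAT period.** Applying Table 2-2 as written:

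| Subject | IAT period ends | Week 52/Early Exit weight |
|---|---|---|
| On first drug at Week 52, no PTA or later PTA entry | Week 52 visit | included |
| On first drug at Week 52, enters PTA that day | day before Week 52 | excluded, although SAP 2.8.4.2 says vital signs are taken before dosing |
| Switched, stays in study | day before first switch | excluded |
| Stopped without switching, stays in study | last dose + 27/1 days | excluded unless Week 52 falls within those days |
| Leaves the study while on first drug | earlier of treatment disposition date and last dose + 27/1 days | included only if Early Exit falls by then |

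I read 27/1 as 27 days for erenumab and 1 day for oral drugs. This is an assumption, but it fits the exposure formulas in SAP 5.6.

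**Step 2: the plan's figures.** The plan gives no figure for on-drug weights. The usable inputs come from the sample size section (Protocol 12.8.1, SAP 3): control rate 0.18, odds ratio 2, 394 and 197 subjects.
- Control odds = 0.18/0.82 = 0.2195. Doubled: 0.439. Erenumab rate = 0.439/1.439 = 0.305, a difference of 12.5% (plan: 12%).
- Total for 90% power: 198 x 3 = 594 with continuity correction, or 196 x 3 = 588 with the null variance in both terms. The plan's 591 lies between them, so the inputs are coherent.

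**Step 3: oral subjects on the first drug at Week 52.** Net benefit requires completing the first treatment and responding, so 0.18 = R x q. Here R is first-drug retention and q is the response rate among completers. Hence R = 0.18/q. The documents do not give q for oral drugs.

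| q (assumed) | R | on first drug at Week 52, of 197 | not on it |
|---|---|---|---|
| 1.00 (limit) | 18% | about 35 | 82% |
| 0.65 | 28% | 55 | 72% |
| 0.50 | 36% | 71 | 64% |
| 0.36 | 50% | 98 | 50% |
| 0.30 | 60% | 118 | 40% |

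For erenumab, the cited one-year retention of 75-80% (Protocol 1.1) gives 296-315 of 394, with 20-25% not on drug. Both sets of figures reflect retention only. The PTA rule in Step 1 would remove further completers in either arm, by an amount the documents do not allow me to estimate.

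**Step 4: offset from Early Exit.** For the share without an on-drug weight to fall to half, a fraction (0.5 - R)/(1 - R) of oral non-completers would have to leave the study on the first drug and be weighed in time. This is 0.39 at R = 18%, 0.31 at 28% and 0.22 at 36%.

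**Step 5: ECG.** Table 8-1 shows one mid-study ECG as well as Week 52. Column alignment is lost in the text, so I take it as about Week 24. Assuming a constant rate of leaving, retention at Week 24 is R^(24/52): 0.45 at R = 18%, 0.56 at 28% and 0.62 at 36%. For erenumab at 75-80% it is 0.88-0.90. The mid-study ECG therefore reaches far more oral subjects on their first drug than the Week 52 one does.

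**The case against.** The best defence is that the phrase means grouping, not restriction. SAP 1.2 and 2.1.1.1 equate initially assigned with randomised treatment. SAP 2.8 says safety summaries are given by initially assigned group unless stated otherwise. SAP 2.8.4.2 does not cite Table 2-2, and Table 2-1 places vital signs by study day. Protocol 12.5.2 also counts data as on-treatment until 112 days after the last dose of any study treatment. On this view switchers' Week 52 weights are already shown by arm.

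This stands as a possible reading, but it does not settle the matter. The sentence in 2.8.4.2 already says by treatment group, so the added phrase may well carry a further meaning. Table 2-2 is titled for safety analysis and defines IAT and switched periods. Table 2-1 itself points to Table 2-2 for safety follow-up and keeps follow-up out of the visit windows. Because Table 2-2 also ends the core phase 27/1 days after the last dose for early stoppers, their Week 52 weight appears to move to follow-up even under the grouping view.

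It is also fair that adverse events are sought at every visit, reasons for switching are summarised (SAP 2.4.1), and oral drugs receive any extra safety measurements in their labels. Weight change that prompts a switch can surface there. A reader might infer that harms of oral drugs are bound to be understated, but the documents do not show that weight drives switching and give no rate of weight change.

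**Conclusion.** The point holds as an undefined analysis rule with a real consequence. Applied as written, Table 2-2 makes the weight summary rest mainly on subjects still on their first drug, or leaving the study while on it. It also drops completers who enter PTA at Week 52. From retention alone, at most 82% of oral subjects would lack an on-IAT Week 52 weight, and about 64-72% if 50-65% of oral completers respond. The larger loss in the oral arm is likely but not certain, because the documents state no oral retention for this population and the PTA rule removes an unknown number in both arms.

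Three stronger readings are tempting and are not supported:
- **That most oral subjects certainly lack an on-drug weight, or that 84-87% do.** The second figure comes from the 13-16% persistence in Protocol 1.1, which is chronic-migraine claims data. It falls below the 18% retention that the plan's own control rate requires. If only 30% of oral completers respond, retention is 60% and the majority claim fails.
- **That only subjects who stayed a year contribute.** Early Exit weights taken in time also count.
- **That the ECG summary is equally affected.** Only its Week 52 part shares the problem fully.

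This is a descriptive safety output. The primary analysis and sample size are unaffected.

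**What to change.** - **SAP 2.8.4.2, and the Week 52 ECG in 2.8.4.1:** make the between-arm summary one of Week 52/Early Exit values for all safety-set subjects by randomised arm, regardless of switching or stopping. State that values after the end of treatment stay in this summary and do not move to safety follow-up.
- **Beside it:** keep an on-IAT table that states its data restriction and shows the number and percentage of each arm contributing.
- **SAP Table 2-2:** amend it, or the way it is used, so that pre-dose Week 52 assessments of PTA entrants count as core-phase and IAT data.
- **Optional, while subjects remain on study:** in Protocol Table 8-1 footnote 1 and Table 8-3, add a body weight at the existing visit where a switch or permanent stop is documented.

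The SAP changes cost some wording and one extra table per parameter, from data already collected. The optional item is new data collection, though only one scale reading at a visit already scheduled. The drawback of the all-subjects summary is that it includes effects of later drugs, which is why the on-IAT table stays beside it.
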